**Table 15: Listing of Non-Serious, Unsolicited, Moderate or Severe Adverse Events**

[Implementation Note: This listing is included in the tables document, as it is included in the body of the abbreviated CSR. If the event is ongoing (no stop date), indicate “ongoing” in the “Duration” column. In the “If Not Related, Alternate Etiology” column, merge the 2 data fields for collecting alternate etiology, separate by a colon. Listing should be sorted by Dose Group, Subject ID, and AE Number.]

Adverse Event	MedDRA System Organ Class	MedDRA Preferred Term	Study Day	Duration of AE in Days	Severity	Relationship to Study Treatment (Alternate Etiology)	Action Taken with Study Treatment	Subject Discontinued Due to AE	Outcome
Dose Group: , Subject ID: , AE Number:									
Comments:									
Dose Group: , Subject ID: , AE Number:									
Comments:									

---

### **14.3.3 Narratives of Deaths, Other Serious and Significant Adverse Events**

(not included in SAP, but this is a placeholder for the CSR)

#### 14.3.4 Abnormal Laboratory Value Listings (by Subject)

**Table 16: Listing of Abnormal Laboratory Results – Chemistry**

[Implementation Note: This listing is included in the table shells document, as it is included in the body of the abbreviated CSR. This listing includes all abnormal Chemistry results (laboratory results outside of the normal range defined in the protocol). Normal chemistry results for other parameters that occurred on the same visit as the abnormal result will not be listed. There is a separate, complete listing of all Chemistry results. In the Laboratory Parameter column, indicate the units (LB.LBSTRESU) after the parameter, e.g., Sodium (mEq/L). This listing is not color-coded. Results that are outside the normal range but not mild, moderate, or severe will have ONR listed as severity. Similarly, results that meet grading criteria of mild, moderate, or severe but which are not treatment emergent (not worse than baseline) will be shown as ONR.]

Sort order: Dose Group, Subject ID, Time Point, and Parameter.]

Dose Group	Subject ID	Sex	Time Point	Date of Assessment	Laboratory Parameter (Units)	Result	Severity

**Table 17: Listing of Abnormal Laboratory Results - Hematology**

[Implementation Note: This listing is included in the table shells document, as it is included in the body of the abbreviated CSR. This listing includes all abnormal Hematology results (laboratory results outside of the normal range defined in the protocol). Normal hematology results for other parameters that occurred on the same visit as the abnormal result will not be listed. There is a separate, complete listing of all Hematology results. In the Laboratory Parameter column, indicate the units (LB.LBSTRS) after the parameter, e.g., Hemoglobin (g/dL). This listing is not color-coded. Results that are outside the normal range but not mild, moderate, or severe will have ONR listed as severity. Similarly, results that meet grading criteria of mild, moderate, or severe but which are not treatment emergent (not worse than baseline) will be shown as ONR..

Sort order: Dose Group, Subject ID, Time Point, and Parameter.]

Dose Group	Subject ID	Sex	Time Point	Date of Assessment	Laboratory Parameter (Units)	Result	Severity

**Table 18: Listing of Abnormal Laboratory Results - Coagulation**

[Implementation Note: This listing is included in the table shells document, as it is included in the body of the abbreviated CSR. This listing includes all abnormal Coagulation results (laboratory results outside of the normal range defined in the protocol). Normal coagulation results for other parameters that occurred on the same visit as the abnormal result will not be listed. There is a separate, complete listing of all Coagulation results. In the Laboratory Parameter column, indicate the units (LB.LBSTRS) after the parameter, e.g., (seconds). This listing is not color-coded. Results that are outside the normal range but not mild, moderate, or severe will have ONR listed as severity. Similarly, results that meet grading criteria of mild, moderate, or severe but which are not treatment emergent (not worse than baseline) will be shown as ONR.]

Sort order: Dose Group, Subject ID, Time Point, and Parameter.]

Dose Group	Subject ID	Time Point	Date of Assessment	Laboratory Parameter (Units)	Result	Severity

**Table 19: Listing of Abnormal Laboratory Results - Urinalysis**

[Implementation Note: This listing is included in the table shells document, as it is included in the body of the abbreviated CSR. This listing includes all abnormal Urinalysis results (laboratory results outside of the normal range defined in the protocol). Normal urinalysis results for other parameters that occurred on the same visit as the abnormal result will not be listed. There is a separate, complete listing of all Urinalysis results. In the Laboratory Parameter column, indicate the units (LB.LBSTRS) after the parameter, e.g., Leukocytes by Microscopy (/hpf). This listing is not color-coded. Results that are outside the normal range but not mild, moderate, or severe will have ONR listed as severity. Similarly, results that meet grading criteria of mild, moderate, or severe but which are not treatment emergent (not worse than baseline) will be shown as ONR.]

Sort order: Dose Group, Subject ID, Time Point, and Parameter.]

Dose Group	Subject ID	Sex	Time Point	Date of Assessment	Laboratory Parameter (Units)	Result	Severity
					Occult Blood by Dipstick	Negative	

## 14.3.5 Displays of Laboratory Results

### 14.3.5.1 Chemistry Results

**Table 20: Chemistry Toxicity Grade by Parameter, Severity, Dose Group, and Time Point**

[Implementation Note: Severity will be graded based on toxicity criteria in protocol. If there is not at least 1 Mild, Moderate, or Severe Event for Max Severity Post-Baseline, then only the Max Severity Post-Baseline row will be shown for the parameter. Toxicities representing an increase in the laboratory result will be summarized separately from decreases.]

Dose Group	Time Point	N	Mild	Moderate	Severe
			n (%)	n (%)	n (%)
Any Parameter					
SAD Any Dose	Baseline	x	x (x)	x (x)	x (x)
	Max Severity Post-Baseline	x	x (x)	x (x)	x (x)
	Day 2	x	x (x)	x (x)	x (x)
	Day 7	x	x (x)	x (x)	x (x)
	Final Visit	x	x (x)	x (x)	x (x)
SAD 1 mg	Baseline	x	x (x)	x (x)	x (x)
	...	x	x (x)	x (x)	x (x)
SAD 10 mg	Baseline	x	x (x)	x (x)	x (x)
	...	x	x (x)	x (x)	x (x)
Placebo	Baseline	x	x (x)	x (x)	x (x)
	...	x	x (x)	x (x)	x (x)
Sodium, Decrease					
SAD Any Dose	Baseline	x	x (x)	x (x)	x (x)
...	...	x	x (x)	x (x)	x (x)
Notes: The “Max Severity Post Baseline” rows indicate the maximum severity experienced by each subject at any time point post baseline, including unscheduled assessments.					
N=Number of subjects in the Safety Population with the laboratory result assessed at the respective time point.					

**Table 21: Chemistry Change from Baseline by Parameter, Dose Group, and Time Point**

Dose Group	Time Point	N	Change from Baseline			
			Mean	SD	Median	Min, Max
Sodium (mEq/L)						
SAD Any Dose	Day 2	x	x	x	x	x, x
	Day 7	x	x	x	x	x, x
	Final Visit	x	x	x	x	x, x
SAD 1 mg	Day 2	x				
	...	x	x	x	x	x, x
SAD 10 mg	Day 2	x				
	...	x	x	x	x	x, x
	...	x	x	x	x	x, x
Placebo	Day 2	x	x	x	x	x, x
	...	x	x	x	x	x, x
Potassium (mEq/L)						
SAD Any Dose	Day 2	x	x	x	x	x, x
	...	x	x	x	x	x, x

Note: N=Number of subjects in the Safety Population with the laboratory result assessed at the respective time point.

#### 14.3.5.2 Hematology Results

**Table 22: Hematology Toxicity Grade by Parameter, Severity, Dose Group, and Time Point**

[Implementation Note: Severity will be graded based on toxicity criteria in protocol. If there is not at least 1 Mild, Moderate, or Severe Event for Max Severity Post-Baseline, then only the Max Severity Post-Baseline row will be shown for the parameter. Toxicities representing an increase in the laboratory result will be summarized separately from decreases.]

This table will repeat Table 20 for Hematology parameters.
--

**Table 23: Hematology Change from Baseline by Parameter, Dose Group, and Time Point**

This table will repeat Table 21 for Hematology parameters.
--

**14.3.5.3 Coagulation Clinical Laboratory Results****Table 24: Coagulation Toxicity Grade by Parameter, Dose Group, and Time Point**

[Implementation Note: Severity will be graded based on toxicity criteria in protocol. If there is not at least 1 Mild, Moderate, or Severe Event for Max Severity Post-Baseline, then only the Max Severity Post-Baseline row will be shown for the parameter. Toxicities representing an increase in the laboratory result will be summarized separately from decreases.]

This table will repeat Table 20 for Coagulation parameters.
---

**Table 25: Coagulation Change from Baseline by Parameter, Dose Group, and Time Point**

This table will repeat Table 21 for Coagulation parameters.
---

**14.3.5.4 Urinalysis Results****Table 26: Urinalysis Toxicity Grade by Parameter, Severity, Dose Group, and Time Point**

[Implementation Note: Severity will be graded based on toxicity criteria in protocol. If there is not at least 1 Mild, Moderate, or Severe Event for Max Severity Post-Baseline, then only the Max Severity Post-Baseline row will be shown for the parameter. Toxicities representing an increase in the laboratory result will be summarized separately from decreases.]

This table will repeat Table 20 for Urinalysis parameters.
--

### 14.3.6 Displays of Vital Signs

**Table 27: Vital Sign Toxicity Grade by Parameter, Severity, Dose Group, and Time Point**

[Implementation Note: If there is not at least 1 Mild, Moderate, or Severe Event for Max Severity Post-Baseline, then only the Max Severity Post-Baseline row will be shown for the parameter.]

Dose Group	Time Point	N	Mild n (%)	Moderate n (%)	Severe n (%)
Any Parameter					
SAD Any Dose	Baseline	x	x (x)	x (x)	x (x)
	Max Severity Post Baseline				
	Day 1, 15 minutes Post-Dose	x	x (x)	x (x)	x (x)
	Day 1, 1 h Post-Dose	x	x (x)	x (x)	x (x)
	Day 1, 2 h Post-Dose	x	x (x)	x (x)	x (x)
	Day 2	x	x (x)	x (x)	x (x)
	Day 4	x	x (x)	x (x)	x (x)
	Day 7	x	x (x)	x (x)	x (x)
	Day 14	x	x (x)	x (x)	x (x)
	Final Visit	x	x (x)	x (x)	x (x)
SAD 1 mg	Baseline	x	x (x)	x (x)	x (x)
	...	x	x (x)	x (x)	x (x)
SAD 10 mg	Baseline	x	x (x)	x (x)	x (x)
	...	x	x (x)	x (x)	x (x)
Placebo	Baseline	x	x (x)	x (x)	x (x)
	...	x	x (x)	x (x)	x (x)
Systolic Blood Pressure, Decrease					
SAD Any Dose	Baseline	x	x (x)	x (x)	x (x)
...	...	x	x (x)	x (x)	x (x)
Notes: The “Max Severity Post Baseline” rows indicate the maximum severity experienced by each subject at any time point post baseline, including unscheduled assessments.					
N = Number of subjects in Safety Population with the vital sign assessed for the respective time point.					

**Table 28: Vital Sign Change from Baseline by Parameter, Dose Group, and Time Point**

Dose Group	Time Point	N	Change from Baseline			
			Mean	SD	Median	Min, Max
Systolic Blood Pressure (mmHg)						
SAD Any Dose	Day 1, 15 minutes Post-Dose	x	x	x	x	x, x
	Day 1, 1 h Post-Dose	x	x	x	x	x, x
	Day 1, 2 h Post-Dose	x	x	x	x	x, x
	Day 2	x	x	x	x	x, x
	Day 4	x	x	x	x	x, x
	Day 7	x	x	x	x	x, x
	Day 14	x	x	x	x	x, x
	Final Visit	x	x	x	x	x, x
SAD 1 mg	Day 1, 15 minutes Post-Dose	x	x	x	x	x, x
	...	x	x	x	x	x, x
SAD 10 mg	Day 1, 15 minutes Post-Dose	x	x	x	x	x, x
	...	x	x	x	x	x, x
Placebo	Day 1, 30 minutes Post-Dose	x	x	x	x	x, x
			x	x	x	x, x
Diastolic Blood Pressure (mmHg)						
SAD Any Dose	Day 1, 15 minutes Post-Dose	x	x	x	x	x, x
..	...	x	x	x	x	x, x

Note: N=Number of subjects in the Safety Population with the laboratory result assessed at the respective time point.

### 14.3.7 Displays of ECG Measurements

**Table 29: ECG Overall Interpretations, Post Dose Compared to Baseline by Dose Group and Time Point**

ECG Interpretation	SAD Any Dose n (%)	SAD 1 mg n (%)	SAD 10 mg n (%)	Placebo n (%)
Day 1, 4 h Post-Dose				
N	x	x	x	x
Normal at Both Times	x (x)	x (x)	x (x)	x (x)
Normal to Abnormal, NCS	x (x)	x (x)	x (x)	x (x)
Normal to Abnormal, CS				
Abnormal, NCS at Both Times	x (x)	x (x)	x (x)	x (x)
Abnormal, NCS to Abnormal, CS				
Abnormal, NCS to Normal	x (x)	x (x)	x (x)	x (x)
Day 7				
N	x	x	x	x
Normal at Both Times	x (x)	x (x)	x (x)	x (x)
...	x (x)	x (x)	x (x)	x (x)
Final Visit				
N	x	x	x	x
Normal at Both Times	x (x)	x (x)	x (x)	x (x)
...	x (x)	x (x)	x (x)	x (x)

Notes: N = Number of subjects in Safety Population with the ECG results assessed at the respective time point.  
CS= clinically significant; NCS= not clinically significant.

**Table 30: ECG Toxicity Grade by Parameter, Severity, Dose Group, and Time Point**

[Implementation Note: If there is not at least 1 Mild, Moderate, or Severe Event for Max Severity Post-Baseline, then only the Max Severity Post-Baseline row will be shown for the parameter.]

Dose Group	Time Point	N	Mild n (%)	Moderate n (%)	Severe n (%)
PR Interval					
SAD Any Dose	Baseline	x	x (x)	x (x)	x (x)
	Max Severity Post Baseline				
	Day 1, 4 h Post-Dose	x	x (x)	x (x)	x (x)
	Day 7	x	x (x)	x (x)	x (x)
	Final Visit	x	x (x)	x (x)	x (x)
SAD 1 mg	Baseline	x	x (x)	x (x)	x (x)
	...	x	x (x)	x (x)	x (x)
SAD 10 mg	Baseline	x	x (x)	x (x)	x (x)
	...	x	x (x)	x (x)	x (x)
Placebo	Baseline	x	x (x)	x (x)	x (x)
	...	x	x (x)	x (x)	x (x)
QTcF Interval					
SAD Any Dose	Baseline	x	x (x)	x (x)	x (x)
	...	x	x (x)	x (x)	x (x)
Notes: The “Max Severity Post Baseline” rows indicate the maximum severity of ECG Results Related to study treatment experienced by each subject at any time point post baseline, including unscheduled assessments.					
N = Number of subjects in Safety Population with the ECG results assessed at the respective time point.					

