All AEs (laboratory and clinical symptoms) will be graded for severity and assessed for relationship to study product (see definitions). Abnormalities present at baseline will not be reported as AEs unless worsening in severity post-dosing. AEs characterized as intermittent require documentation of onset and duration of each episode. The start and stop date of each reported AE will be recorded on the appropriate DCF and eCRF. For vital sign AEs, when multiple readings are taken within the same day the AE of highest severity will be documented to allow an assessment of the duration of the AE from the highest level of intensity. If a subject was enrolled in the trial with a laboratory value that is outside the reference range, but within the acceptable ranges, an AE will be recorded if it otherwise meets the definition of AE in [Section 8.1.1](#) and the on-study value is higher (if initially high) or lower (if initially low) than the screening value.

Severity of Event:

AEs will be assessed by the Site PI using a protocol-defined grading system ([Appendix B](#)). For events not included in the protocol-defined grading system, the following guidelines will be used to quantify severity:

Mild (Grade 1): Events that are usually transient and may require only minimal or no treatment or therapeutic intervention and generally do not interfere with the subject's usual activities of daily living,

Moderate (Grade 2): Events that are usually alleviated with additional specific therapeutic intervention. The event interferes with usual activities of daily living, causing discomfort but poses no significant or permanent risk of harm to the subject,

Severe (Grade 3): Events interrupt usual activities of daily living, or significantly affects clinical status, or may require intensive therapeutic intervention. Severe events are usually incapacitating.

Relationship to Study Product: The assessment of the AE's relationship to study product will be done by the licensed study physician indicated on Form FDA 1572 and the assessment will be part of the documentation process. Whether the AE is related or not, is not a factor in determining what is or is not reported in this trial. If there is any doubt as to whether a clinical observation is an AE, the event should be reported.

In a clinical trial, the study product must always be suspect. The relationship to study product will be assessed for AEs using the terms related or not related:

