10.5.2 Clinical Safety Labs, Vital Signs, and Electrocardiograms

Baseline for clinical safety labs, vital signs, and ECGs will be defined as the last result obtained before the dose of study product. For crossover data, there will be a separate baseline for each treatment. Changes from baseline for clinical safety labs, vital signs, and ECGs results will be summarized by dose group and time point. Clinical safety labs and vital signs will be graded ([Appendix B](#)) and summarized by severity, group, and visit. Rules for analyzing replicates for a safety time point (labs, vital signs, ECG), if obtained, will be described in the SAP.

Treatment-emergent abnormal laboratory test results will be identified. Treatment-emergent abnormal laboratory tests are tests for which the result was not graded as mild or worse at baseline but graded as mild or worse after dosing. Laboratory tests graded as mild at baseline, but moderate or worse any time after dosing will also be regarded as treatment-emergent abnormal laboratory test results.

ECG measurements will include heart rate, RR interval, QT interval, QTcF interval, PR interval, and QRS duration. Baseline for ECG measurements is defined per protocol as the value pre-dosing on Day 1 (or pre-dosing on Day 21 for period 2 of Part 3). Change from baseline will be summarized descriptively by regimen at each scheduled evaluation. QTc results will be summarized categorically according to the ICH Guideline E14 “Clinical Evaluation of QT/QTc Interval Prolongation and Proarrhythmic Potential for Non-Antiarrhythmic Drugs” (October 2005):

- QTcF >450 ms, males only
- QTcF >470 ms, females only
- QTcF >480 ms
- QTcF >500 ms
- QTcF increases from baseline by at least 30 ms but less than 60 ms
- QTcF increases from baseline by at least 60 ms

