Appendix B. TOXICITY TABLE

Clinical Adverse Events			
VITAL SIGNS	Mild (Grade 1)	Moderate (Grade 2)	Severe Grade 3
Fever - °C	38.0-38.4	38.5-38.9	>38.9
Tachycardia - bpm	101-115	116-130	>130 or ventricular dysrhythmias
Bradycardia – bpm • Baseline ≥60 OR, if Baseline <60	• 50-54 OR, if Baseline <60, • 45-50	• 45-49 OR, if baseline <60, • 40-44	• <45 OR, if baseline <60 • <40
Hypertension (systolic) - mmHg	141-150	151-160	>160
Hypertension (diastolic) - mmHg	91-95	96-100	>100
Hypotension (systolic) - mmHg	85-89	80-84	<80
Tachypnea – breaths per min	23-25	26-30	>30
CARDIOVASCULAR	Mild (Grade 1)	Moderate (Grade 2)	Severe Grade 3)
Arrhythmia		Asymptomatic; transient signs; no medical intervention required	Recurrent/persistent; symptomatic medical intervention required
Hemorrhage, Blood Loss	Estimated blood loss ≤100 mL	Estimated blood loss >100 mL; no transfusion required	Transfusion required

QTc (Fridericia's correction) ¹	Asymptomatic, QTc interval 450-479 msec	Asymptomatic; QTc interval 480 to 499 msec OR Increase in interval 30-59 msec above baseline	Asymptomatic; QTc interval \geq 500 msec OR Increase in interval \geq 60 msec above baseline
PR Interval (prolonged) ¹	PR interval 0.21-0.25 sec	PR interval >0.25	Type II 2 nd degree AV block OR Ventricular pause >3.0 sec
RESPIRATORY	Mild (Grade 1)	Moderate (Grade 2)	Severe (Grade 3)
Cough	Transient; no treatment	Persistent cough	Interferes with daily activities
Bronchospasm, Acute	Transient; no treatment; FEV1 71-80% of predicted peak flow	Requires medical intervention; normalizes with bronchodilator; FEV1 60-70% of predicted peak flow	No normalization with bronchodilator; FEV1 $<60\%$ of predicted peak flow
Dyspnea	Does not interfere with usual and social activities	Interferes with usual and social activities; no treatment	Prevents daily and usual social activity OR requires treatment
GASTROINTESTINAL	Mild (Grade 1)	Moderate (Grade 2)	Severe (Grade 3)
Nausea	No interference with activity	Some interference with activity	Prevents daily activities
Vomiting	No interference with activity OR 1-2 episodes/24 hours	Some interference with activity OR >2 episodes/24 hours	Prevents daily activity OR requires IV hydration OR requires medical intervention

¹Inclusion dependent upon protocol requirements.

Diarrhea	2-3 loose or watery stools or <400 g/24 hours	4-5 loose or watery stools or 400-800 g/24 hours	≥6 loose or watery stools or >800g/24 hours OR requires IV hydration OR requires medical intervention

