## 7.8. 12-Lead Standard Electrocardiogram

All 12-lead standard ECG measurement results, overall interpretation, and findings will be listed in [Listing 20](#), [Listing 21](#), and [Listing 22](#).

12-lead standard ECG results will be summarized in tables and figures:

- Tabularly, 12-lead standard ECG change in overall interpretation from baseline will be shown by Dose Group and time point ([Table 29](#)).
- Tabularly, by parameter, Dose Group, time point, and toxicity grade (including maximum severity post-baseline) ([Table 30](#)).
- Tabularly, by summary statistics for change from baseline, reported by parameter, Dose Group, and time point ([Table 31](#)).
- Tabularly, by Dose Group, time point, and sex based on QTcF categories according to the ICH Guideline E14 “Clinical Evaluation of QT/QTc Interval Prolongation and Proarrhythmic Potential for Non-Antiarrhythmic Drugs” (protocol v6.0 Section 10.5.2). ([Table 32](#)).
- Graphically, using box plots of change from baseline by parameter, Dose Group, and time point ([Figure 54](#), [Figure 55](#), [Figure 56](#), [Figure 57](#), [Figure 58](#), [Figure 59](#)).

The following parameters will be presented (in order): PR interval, QRS duration, QT interval, QTcF interval, RR interval, and mean ventricular rate.

Unscheduled 12-lead standard ECG measurements will be listed but excluded from tabular and graphical summaries. Individual interval measurements will be presented in listings along with overall interpretation

and comments. Other ECG findings besides interpretation will also be included in listings. Repeated ECG due to clinic error or technical problem will be used for all analyses instead of the original ECG result. Additional ECG measurements taken as follow-up for safety will be included in listings and in computing maximum severity post baseline, but not as separate time points in summary tables. For repeats that were done due to delayed dosing, the median of the last triplicate ECG measurement prior to dosing will be considered as baseline for that subject.

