**Figure 17: Proportions of Subjects with Related Adverse Events by Dose Group, MedDRA SOC, and Severity**

[Implementation Note: This figure includes serious and non-serious unsolicited adverse events deemed related to study product. Note that this figure will present the number of subjects with types of adverse events, and a subject may not be counted more than once for the same type of adverse event but will be counted only once for the maximum severity of the respective type. Each figure panel will show counts for all SOCs observed in any Dose Group during the study (as a related AE). If the number of SOCs is too large to fit in 2 rows of panels, then this figure will be split into multiple figures in the CSR, with 1 row of 2 panels in each figure. SOCs will be ordered alphabetically.]

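### The Table 30 footnote restricts the ECG maximum-severity row to treatment-related results, a filter that SAP 7.8 and the matching laboratory and vital-sign tables do not have

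*SAP*

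**What the plan says.** SAP Table 30 summarizes ECG parameters by toxicity grade, dose group and time point. Its footnote defines the maximum-severity row as the "maximum severity of ECG Results Related to study treatment experienced by each subject at any time point post baseline, including unscheduled assessments". Its implementation note adds that if that row contains no Mild, Moderate or Severe event, "then only the Max Severity Post-Baseline row will be shown for the parameter".

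The text that commissions the table, in SAP 7.8, is "Tabularly, by parameter, Dose Group, time point, and toxicity grade (including maximum severity post-baseline". It does not mention relatedness. SAP 5.1 sets the denominator for the maximum-severity row, ECGs included, as the subjects with an observed post-dose result for the parameter.

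The corresponding note in Table 27 (vital signs) says that the "rows indicate the maximum severity experienced by each subject at any time point post baseline, including unscheduled assessments". Table 20 (chemistry) has the same wording, and Tables 22, 24 and 26 repeat Table 20.

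On unscheduled ECGs, SAP 7.8 makes two statements. One lists them but keeps them out of tables and figures. The other counts additional ECGs taken as safety follow-up towards maximum severity. SAP 7.6 and 7.7 also keep unscheduled laboratory and vital-sign results out of summaries, but with an express exception for maximum severity.

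**The concern.** A worst-grade row should be at least as severe as any post-dose visit row for the same subjects. A relatedness filter on that row alone breaks this, and no such judgement is recorded on an ECG measurement. Protocol 8.1.1 says "The relationship to study product will be assessed for AEs using the terms related or not related", and the ECG listings (Listings 20 to 22) have no relatedness column. A graded value that was never reported as an adverse event therefore cannot meet the condition.

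Filters of this kind belong to the adverse-event displays. Figure 17, for example, states: "This figure includes serious and non-serious unsolicited adverse events deemed related to study product".

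The protocol includes ECGs among its primary safety assessments, and Table 30 is the only summary that shows PR by grade. At stake is a worst-grade row that reads zero when a graded value was measured.

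**Working it through.** The plan states no figure to reproduce, so the check compares texts and adds a small count.

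**Is the filter supported elsewhere?**

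| Place | Relatedness condition on maximum severity? |
|---|---|
| Table 30 footnote | Yes |
| Table 20 footnote (repeated for Tables 22, 24, 26) | No |
| Table 27 footnote | No |
| SAP 7.8 bullet for Table 30 | No |
| SAP 5.1 denominator | No |

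The numerator is restricted and the denominator is not.

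**What the two Table 30 instructions do together.** If some other value for the parameter passes the filter, the visit rows stay and can show a worse grade than the maximum row. If none passes, the visit rows are hidden and the measured grade is absent from the table.

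**Illustration.** Group sizes are the planned ones in Protocol 3.1.1.1: 3 active at 1 mg and 6 active at 10 mg, so 3 + 6 = 9 for any dose. The SAP does not give actual enrolment. Both cases assume that the value was not reported as an adverse event and that no other value for the parameter is graded.

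*Case A, PR.* One 10 mg subject has a Day 7 PR of 0.22 sec. Protocol Appendix B grades "PR interval 0.21-0.25 sec" as Mild.
- With the filter, the maximum row is 0/6 (0%) at 10 mg and 0/9 for any dose, and the Day 7 row is hidden.
- Without it, the maximum row is 1/6 = 17% at 10 mg and 1/9 = 11% for any dose. The same event at 1 mg would be 1/3 = 33%.

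*Case B, QTcF.* A woman at 10 mg has a Day 7 QTcF of 460 ms from a baseline of 440 ms, a rise of 460 − 440 = 20 ms. Appendix B grades 450 to 479 ms as Mild. Against the six Table 32 categories:
- above 450 ms, male: not applicable
- above 470 ms, female: no
- above 480 ms: no
- above 500 ms: no
- rise of 30 to under 60 ms: no
- rise of 60 ms or more: no

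She meets 0 of 6, so Table 32 does not pick her up, and 0/6 against 1/6 applies in Table 30 as well. By contrast, a scheduled QTcF of 485 ms meets the sex-specific category and the 480 ms category, so at least 2 of 6.

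**Unscheduled ECGs.** The footnote counts all of them. SAP 7.8 counts those taken as safety follow-up, a term it does not define. The two rules differ only for an unscheduled ECG that is not safety follow-up.

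**The case against.** The case for leaving this alone has several parts.

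- Table 30 is an addition made by the SAP. Protocol 10.5.2 calls for laboratory results and vital signs to be graded, but for ECGs it says "Change from baseline will be summarized descriptively by regimen at each scheduled evaluation" and then lists QTcF categories. Those are Tables 31 and 32, and neither is filtered. This stands, and it limits the impact.
- Other displays remain. Table 29 shows shifts in overall interpretation without a filter, so a Day 7 ECG read as abnormal would appear there, though not by parameter or grade. Listing 20 shows every ECG with its grade. A value reported as an adverse event appears in Table 13 and Listing 10 whatever its relatedness. This stands too.
- Appendix B places the PR and QTc grades under clinical adverse events, so a graded value might be reported as one. The documents do not say that every graded ECG is automatically an adverse event, so the premise of Cases A and B is possible but not certain.
- A programmer would find no relatedness variable for an ECG and would probably ignore the phrase. That is likely, but it relies on the shell not being followed.

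A reader might also infer that the footnote brings in unscheduled ECGs that SAP 7.8 rules out altogether. The text does not support that, because 7.8 itself counts safety follow-up ECGs in maximum severity. Under Protocol 6.7, unscheduled visits are made at the investigator's direction for follow-up and include safety assessments. An ECG at a visit prompted by an injection-site change is plausibly of that kind, so the two rules may well agree on it.

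**Conclusion.** The footnote is wrong as written. Its relatedness filter has no basis in SAP 7.8, SAP 5.1 or the parallel tables, and no recorded variable to act on. Together with the row-hiding note, it can remove a measured PR or QTcF grade from Table 30.

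The size is small. In the illustration, one subject's grade shows as 0% instead of 17% at 10 mg, or instead of 11% for any dose. This rests on the planned group sizes, on the value not being reported as an adverse event, and on no other graded value for that parameter. The report is descriptive and abbreviated.

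A reader might infer that ECG safety findings would be lost, or that the primary safety assessment is undermined. The documents do not support this: the ECG summaries that the protocol specifies are unfiltered, and every value is listed with its grade. The difference over unscheduled ECGs is real but narrow and secondary. This is a low-priority correction that is worth making because it costs almost nothing.

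**What to change.** In the Table 30 footnote, strike the phrase that limits the row to treatment-related ECG results, so that it matches Tables 20 and 27. In SAP 7.8, add to the sentence on unscheduled ECGs the exception for calculating maximum severity that SAP 7.6 and 7.7 already carry; the footnote and the text then agree. The cost is one phrase removed and one clause added, with no new data, collection or table.
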